10.5 Outcomes

All oral rinse products are commercially available, low risk products. Therefore, adverse outcomes are anticipated to be extremely rare, and will be reviewed weekly by the study team/committee. Any adverse event will be documented in our CDART database system.

The primary and secondary outcomes of RT-PCR (RQ), viral infectivity (RF), and cytokine/chemokine analyte concentration (pg/mL) for each sample type and each participant will be stored as a comma-separated values file analyzed using Excel (or similar) software. This data will be available to research study personnel weeks to months after sample collection when the experiments are conducted. Samples will be run in batches resulting in large spreadsheets of data. Periodontal exam data will be entered into CDART and can be exported as a comma-separated values file.

The outcomes do not include patient treatment response, and therefore the outcomes will not be reviewed and adjudicated by an outside committee. The study personnel will constitute their own committee that meets weekly, and they will review and evaluate the data once these experiments are conducted. The committee will not be masked to the participant's group assignment; the statistician will conduct analyses and then the committee will evaluate the data to reach scientific conclusions on which mouthrinse is more effective.

10.5.1 Primary Outcome

The primary objective of this study is to determine the efficacy of antiseptic mouthwashes on reducing SARS-CoV-2 cellular infectivity in participant saliva. *We hypothesize that COVID-19+ patients will have a >20% reduction in SARS-CoV-2 viral infectivity following a 60 second oral rinse with an antiseptic mouthrinse and that this reduction will persist for at least 30 minutes.* This primary objective will focus on quantifying SARS-CoV-2 viral infectivity and mRNA level using an *in vitro* infectivity assay (Reduction factor (RF) calculated from PFU/mL) and RT-PCR (relative quantification [RQ] ratio). This objective provides urgently needed data to guide healthcare workers on the proper use of specific commercially available mouthwashes capable of reducing SARS-CoV-2 viral infectivity and potentially limiting COVID-19+ transmission.

Outcome assessments will be conducted weeks to months after the study visit, when RT-PCR and viral infectivity assays are routinely conducted in the COVID Core and the laboratory of [name], respectively.

10.5.2 Secondary Outcomes

The secondary objectives are to measure inflammation-associated cytokine and chemokine concentration (pg/mL) in saliva and blood samples taken from SARS-CoV-2+ participants and also to determine the frequency of periodontal disease among participants. *We hypothesize that SARS-CoV-2+ participants using Colgate oral health products will have lower blood and salivary inflammation-associated cytokine and chemokine concentrations (pg/mL) than non-intervention controls. Furthermore, we hypothesize that SARS-CoV-2+ participants will have a greater incidence of periodontal disease than the general population.* Outcome assessments will be conducted weeks to months after the study visit, when statistical analyses are conducted.

10.5.3 Tertiary Outcomes

The tertiary outcomes of this study are a periodontal exam and post-rinse surveys to evaluate patient perceptions of the mouthrinse, their symptoms and feedback on their willingness to use the product. Percentage of respondents will be gathered and reported for surveys. Periodontal exam data will be evaluated and the periodontal status for each participant will be assigned via the case definitions for periodontitis, gingivitis, and clinical periodontal health as described in the 2017 World Workshop on the Classification of Periodontal and Peri-Implant Diseases and Conditions and the 2012 Centers for Disease Control and Prevention and American Academy of Periodontology case definitions.^{19, 20} Patients' final periodontal status will be the tertiary outcome of the periodontal exam and will be reported as the percentage of participants categorized into each diagnostic group. These tertiary outcomes are exploratory and therefore have no hypotheses assigned to them.

Table: Study Variables and Covariates

X Independent variables	Y Dependent variables for primary and secondary outcomes	Covariates
Mouthrinse Group	Viral infectivity (continuous positive variable)	Age (years)
Time (in minutes, 0, 15, 30, 45 and 60 minutes, visit 1 and 2)	Viral load (continuous positive variable)	Gender (m/f)
	Cytokine level (continuous positive variable)	Race (White, Native Hawaiian or other pacific islander, Asian, African American, Hispanic or Latino, American Indian or Alaska Native)
		BMI Body mass index (continuous range: 0-56)

10.6 Data Analyses

qRT-PCR: Data will be presented as mean (standard deviation) for normally distributed data and as median [Interquartile range] for non-normally distributed data. P values will be reported as two tailed. Between group comparisons will be performed using a Student's T test or Mann-Whitney test. Normality will be assessed using the Kolmogorov-Smirnov test, and logistic regression will be performed with robust standard errors. Methods adapted from Bullard *et al* 2020.

Viral infectivity: The viral infectivity analysis will compare infectivity levels between mouth rinse types and across the time course for calculation of the reduction factor (RF). The RF will be calculated as the difference in the quotient of the infection titre before ('control titration') and after the mouthrinse ('remaining virus'). Therefore, the log₁₀ titre and its (double) standard deviation (SD) were calculated as well as the variance of the RF.

Inflammatory Markers: Inflammation-associated cytokine and chemokine concentrations (IL-6, CXCL-10, IL-8, and IL-10 [pg/mL]) will be quantified from saliva and blood samples collected at each visit and across the salivary collection time course using multiplex analyte analysis (Luminex technology) and using internal, manufacturer supplied standards of known concentration (pg/mL).

The analysis plan will include use of sensitivity analyses to evaluate the robustness/fragility of the study's main results to reasonable perturbations of the statistical methods and assumptions used in the main analysis. We will first describe the demographics (age, race, sex and BMI) for each study arm. If significant differences are found between groups, we will adjust the remainder of the analysis. The main analysis will be a repeated measures linear regression model(s). If multiple demographics are found to be significantly different the propensity scores will be created and final models will be adjusted by propensity scores. In the primary analysis, viral load and replication as measured by changes in genomic, strand, and subgenomic expression, will be evaluated and compared between treatment groups. Repeated measures linear regression models will be utilized to look at changes in viral load logarithmically before and after treatment. Similarly,

in the secondary analyses, the repeated measures linear regression will be used to compare the changes in other continuous outcomes (such as immunological parameters) from baseline to specific time points outlined. Statistical significance will be tested using a two-sided 0.05 level with adjustments for multiple testing. Multiple testing correction will be made by Tukey adjustments (for multiple study arms) and False Discovery Rate (FDR) where appropriate (i.e. multiple inflammatory markers).

All statistical estimates of population parameters will be tabulated along with corresponding confidence intervals (CIs) and/or standard errors (SEs) to convey level of precision. All P- values will be reported as continuous numerical outputs (and not as dichotomous results). All hypothesis tests yielding large p-value (e.g., $p > \alpha$) will be reported as being inconclusive.

Power Calculation: Using data from Meiller *et al.* we calculated power at four time points.¹⁸ Time points included: Post-0 (immediately post rinse), Post-30 (30 min post rinse), and Post-60, (60 min post rinse). In addition, we calculated a Post-45, which was the midpoint between 30 and 60 min in the Meiller *et al.* data. Based on this viral study evaluating mouth rinse efficacy against infectivity of Herpes Simplex Virus, an enveloped virus, power calculations were determined to estimate effect size and determine sample size as a function of length of mouth rinse time course.¹⁸ The sample size was justified by a paired t-test on outcomes between time points. With three simultaneous comparisons (t_1-t_0 , t_2-t_1 , t_2-t_0) over 30 min, an $n=16$ sample size can detect the effect size in Cohen's $d=0.7$, which is between medium and large, with 80% power and 0.016 type-I error rate by Bonferroni correction. Therefore, with four simultaneous comparisons (t_0-t_1 , t_0-t_2 , t_0-t_3 , t_0-t_4) the sample size required for each arm is ~25 participants per group to discern oral rinse efficacy at any given time point (minutes post rinse).

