The primary objective of this study is to determine the efficacy of antiseptic mouthwashes on reducing SARS-CoV-2 cellular infectivity in COVID+ patient saliva. *We hypothesize that SARS-CoV-2+ patients will have a >20% reduction in SARS-CoV-2 viral infectivity following a 60 second oral rinse with an antiseptic mouthrinse and that this reduction will persist for at least 30 minutes.* This primary objective will focus on quantifying SARS-CoV-2 viral infectivity (Reduction Factor (RF) calculated from plaque forming units [PFU] / mL) and viral titer (Relative Quantification (RQ) ratio) using an *in vitro* infectivity assay and RT-PCR. This objective provides urgently needed data to guide healthcare workers on the proper use of specific commercially available mouthwashes capable of reducing SARS-CoV-2 viral infectivity and potentially limiting SARS-CoV-2+ transmission.

1.2 Secondary Objective:

The secondary objectives are to measure cytokine and chemokine levels (pg/mL) in samples taken from SARS-CoV-2+ patients and also to determine the frequency of periodontal disease among SARS-CoV-2+ patients. *We hypothesize that SARS-CoV-2+ patients using Colgate oral health products will have lower inflammatory marker levels than controls. Furthermore, we hypothesize that SARS-CoV-2+ patients will have a greater incidence of periodontal disease than the general population.*

1.3 Tertiary Objective (*Exploratory*):

The tertiary objective of this study is to use post-rinse surveys to evaluate patient perceptions of the mouthrinse and feedback on their willingness to use the product (units: percentage of respondents). Additionally, a periodontal exam will be performed to assess periodontal health. Patients' final periodontal status will be the tertiary outcome of the periodontal exam and will be reported as the percentage of participants categorized into each diagnosis. This tertiary outcome is exploratory.

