Data generated from the RT-PCR assays (relative quantification (RQ) ratio, numerical value) will be presented as mean (standard deviation) for normally distributed data and as median [Interquartile range] for non-normally distributed data. P values will be reported as continuous numerical scales, with multiple testing adjustments. After performing the main analysis using a linear model specified a priori, various sensitivity analyses will be performed. These will include an analysis of residuals which will rely on graphical methods, examination of skewness, kurtosis, and other descriptive statistics. The sensitivity analyses may also include a Shapiro-Wilk test of the null hypothesis H_0 ‘the underlying distribution of the residuals is Gaussian’. The sensitivity analyses may also include assessment of the impact of using a modified version of the linear model analysis in which the scale of the dependent variable is transformed (e.g., log10 or some other Box-Cox transformation). The sensitivity analyses will be used only to guide our level of trust in the main results.

For the primary analysis, viral infectivity and viral load, we will first determine if these variables are normally distributed. However, we anticipate these variables to be right skewed. They will be log transformed if they are not normally distributed. We will then compare the demographic variables (age, race, sex, age and BMI) and groups (study arms). We will use Chi-square and ANOVA statistics to determine if the demographic variables are evenly distributed amongst the groups. If not we will adjust for these variables in subsequent analyses. In the rare event there are multiple demographic variables that are found to be significantly different by group we will create a propensity score to adjust for these variables in subsequent analyses.

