10.4 Study Stopping Rules

Analysis will occur at several points, while enrolling and collecting samples from 125 patients, in batches of 25 randomized participants. Analysis will occur after enrollment of 25, 50, 100 and then 125 participants and will include viral load and replication (as measured by changes in genomic, strand, and subgenomic expression and will be evaluated and compared between treatment groups). No interim analyses of data will be performed. mRNA obtained from salivary samples will be analyzed and will be assessed by RT-PCR at time points 0 and 30 min. Infectivity assays will be subsequently performed on salivary samples collected at time points 0 min ('baseline') and 30 min post rinse with cycle threshold of 22 or lower (CT22) as determined by RT-PCR using primers specific for SARS-CoV-2 viral products. If the cycle threshold is above 22 (CT22), samples are considered to contain insufficient virus for use in viral infectivity assays. This cycle threshold has been empirically determined by the [name] laboratory (personal communication, [name]).

If saliva samples from patients 6-7 days post-diagnosis are found to routinely have insufficient viral load at interim analysis (at n=25 or 50), the study will be modified for more stringent enrollment criteria (with inclusion up to 5 days post-diagnosis rather than 7, as salivary viral load diminishes with time after infection). Because all oral rinse products are commercially available, low risk products that have previously undergone extensive safety testing and approval procedures, we do not anticipate a situation where safety concerns to participants necessitates halting the study. Adverse events will be reported and reviewed by our internal quality control committee. Medical problems that occur in our facility will be reported as needed to the IRB board and emergency medical personnel will be contacted to care for the patient and potentially bring them to the adjacent UNC medical hospital. If a significant number of adverse events or reactions are witnessed (defined as more than 1 per 20 patients), a safety review will be triggered and study personnel will look at the records in an unblinded fashion to see if one mouthrinse is causing reactions. If that is the case, the mouthrinse study arm associated with adverse events will be discontinued, but the mouthrinse arms associated with minimal adverse events will continue.

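### Infectivity and viral load are both called primary, the RNA measure is described in two ways, and no rule covers error across endpoints: about 7–10% for two endpoints, about 10–19% if three RNA readouts are tested separately

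*Combined protocol and SAP*

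**What the plan says.** **Which outcome is primary.** Section 1.1 opens with infectivity: "The primary objective of this study is to determine the efficacy of antiseptic mouthwashes on reducing SARS-CoV-2 cellular infectivity in COVID+ patient saliva". It then says that the objective will be addressed with both an infectivity reduction factor (RF) and an RT-PCR relative quantification (RQ) ratio, and 10.5.1 repeats this. The central hypothesis in 10.2 Research Hypotheses concerns infectivity alone: a reduction of more than 20% lasting at least 30 minutes.

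Under Primary Outcomes in the same section, both measures are primary: "For the primary analysis, viral infectivity and viral load, we will first determine if these variables are normally distributed". The next paragraphs make the primary analysis a set of ANCOVA models on infectivity, one per post-rinse time. Section 10.6 gives a different account of the primary analysis, namely that "viral load and replication as measured by changes in genomic, strand, and subgenomic expression, will be evaluated and compared between treatment groups".

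**What the RNA measure is.** Sections 1.1, 3 and 10.5.1 speak of one RQ ratio. The variable tables under Primary Outcomes and in 10.5.3 list one viral-load variable. Sections 10.4 and 10.6 name three expression measures; the batch analyses in 10.4 "will include viral load and replication (as measured by changes in genomic, strand, and subgenomic expression".

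**Multiplicity.** Section 10.6 states: "Statistical significance will be tested using a two-sided 0.05 level with adjustments for multiple testing". It continues: "Multiple testing correction will be made by Tukey adjustments (for multiple study arms) and False Discovery Rate (FDR) where appropriate (i.e. multiple inflammatory markers". For the RT-PCR data, Primary Outcomes says: "P values will be reported as continuous numerical scales, with multiple testing adjustments". No method or family is attached to that promise. Bonferroni appears only in the sample-size text, where it covers comparisons between time points.

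**The concern.** Two sections name different primary analyses, and nothing gives an order of testing, a co-primary rule or a split of the 0.05 between endpoints. The corrections that are named work within an endpoint (across arms) or on other outcomes (inflammatory markers). A reader following the plan has no instruction that holds the error at 0.05 across infectivity and RNA.

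The order matters because the two measures may disagree. Sections 2.1 and 2.2 propose that the rinses act by disrupting the viral membrane. It is a fair inference that infectivity could then fall while RNA stays detectable. The plan does not say what the trial would conclude in that case, or if RNA moved and infectivity did not. Under 10.5, a committee that is not masked to group decides which rinse is more effective, so the ranking should be fixed beforehand.

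**Working it through.** **Inputs from the documents:** two-sided 0.05 and Tukey across arms (10.6); five arms with 25 complete participants each (section 3); two endpoints (Primary Outcomes, 10.5.1), or four if the three RNA readouts in 10.4 and 10.6 are tested separately beside infectivity.

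**Input assumed:** the correlation ρ between endpoints in the same person. The documents give none, so I use 0 to 0.9.

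**1. The plan's own figures.** The plan gives no error rate across endpoints to reproduce. Its Bonferroni sizing reproduces closely for four comparisons: 0.05/4 = 0.0125, and with d = 0.7 carried over, a two-sided paired t-test needs 26 for 80% power and has 78.0% at 25, against a stated value of about 25. That correction counts time comparisons within an arm and does not touch endpoints.

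**2. Independent endpoints, each at 0.05.**
- Two: 1 − 0.95² = 9.75%.
- Four: 1 − 0.95⁴ = 18.5%.

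**3. Equally correlated endpoints, one two-sided normal test each.** With c = 1.96 and k endpoints, the error is 1 − ∫ φ(x)·[Φ((c − √ρ·x)/√(1−ρ)) − Φ((−c − √ρ·x)/√(1−ρ))]^k dx.

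**4. The plan's Tukey test within each endpoint.** Simulation with no true effect: five arms of 25, Tukey studentized range at 0.05 for each endpoint, any rejection counted, 40,000 trials per setting (simulation error about 0.2 percentage points).

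| ρ | Two, formula | Two, Tukey | Four, formula | Four, Tukey |
|---|---|---|---|---|
| 0 | 9.75% | 9.7% | 18.5% | 18.6% |
| 0.5 | 9.1% | 9.3% | 15.6% | 16.2% |
| 0.8 | 7.8% | 7.9% | 11.4% | 11.9% |
| 0.9 | 7.0% | 7.2% | 9.4% | 9.9% |

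**5. Unequal correlation.** If the RNA readouts correlate at 0.9 with each other and 0.5 with infectivity, the Tukey simulation gives 12.4% for four endpoints.

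**6. What a rule across endpoints would do.** Splitting the level equally between two independent endpoints gives 1 − 0.975² = 4.9%.

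None of these figures includes the separate ANCOVA at each post-rinse time, which would add to them.

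**The case against.** The strongest reply is that infectivity is plainly the lead. The first sentence of the objective, the central hypothesis and the primary ANCOVA all name it alone. That stands as a statement of emphasis. It is not a testing order, and sections 1.1 and 10.5.1 also place the RT-PCR measure inside the primary objective. If infectivity leads, the wording in 10.6 conflicts with it and needs correcting anyway.

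A second reply is that adjustment is promised, both in 10.6 and for the RT-PCR p-values. This also stands in part. A reader might infer that each primary endpoint is deliberately given its own full 0.05; the documents do not say so. The adjustment across endpoints is unspecified, and the figures above show what follows if only the named corrections are applied.

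A third reply is that no success rule is written. A reader might infer that a rinse will be declared effective on whichever endpoint reaches significance. Section 10.6 does not say that: p-values are to be reported as continuous values and large ones called inconclusive. It does keep a 0.05 level, however, and calling results above alpha inconclusive is itself a threshold. The error rate therefore still has meaning, provided it is read as conditional on that threshold.

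**Conclusion.** The concern holds as a conflict in the plan with a moderate effect on error control. Infectivity and viral load are both primary without an order, two sections name different primary analyses, and no stated method covers error across them. With 0.05 and Tukey per endpoint, the chance of at least one false arm difference is about 7–10% for two endpoints, the better-supported count. It is about 10–19% if the three RNA readouts are tested separately. Both ranges rest on assumed correlations from 0.9 to 0 and omit repeat testing over time. Every case computed exceeds 5%.

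A reader might infer a single figure of about 16% from a plan with four primary endpoints. The documents do not support that. It needs a correlation near 0.46 to 0.5, which they do not give, and it reads the three expression terms as separate endpoints when the objective, 10.5.1 and the variable tables define one RNA variable. The text is inconsistent about the RNA outcome; it does not clearly set up a four-endpoint family.

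**What to change.** Amend 1.1, Primary Outcomes, 10.5.1 and 10.6 together:

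- Make infectivity RF the first-ranked primary endpoint, in line with the central hypothesis, at one stated time point, with Tukey for the comparisons between rinse arms. Thirty minutes is a natural candidate: the hypothesis names it, and 10.4 plans both assays then.
- Define RQ once, from a single RNA target chosen by the sponsor, and test it second at 0.05 only if infectivity is significant.
- Label the other RNA readouts and time points supportive or exploratory.
- Reword the 10.6 sentence that places RNA expression in the primary analysis, and align 10.4 with it.

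State the gate pair by pair: the RNA difference between two arms is tested only if the infectivity difference between the same two arms is significant. If nothing works, the error stays at 0.05, because RNA is reached only through a false infectivity finding. If some rinses work and others do not, each pair can add at most its own per-pair level. For Tukey with five arms of 25 that level is 2·P(t₁₂₀ > 3.917/√2) = 0.0065, so the ten pairs give a bound of 10 × 0.0065 = 6.5%. Using 0.05/10 = 0.005 per pair brings the bound to 5%.

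The cost is wording only, with no new data. There are two downsides. An effect on RNA without one on infectivity could no longer be a primary success. Infectivity is assayed only in samples with CT of 22 or lower (sections 3 and 10.4), so the lead endpoint may have fewer than 25 evaluable participants per arm.

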The primary analysis will be ANCOVA models with viral infectivity at time Post 0 minute, Post 1 minute, post 15 minute, post 30 minute, post 45 minute and post 60 minute adjusting for time Pre 0 minute. We will also perform a repeated measures analysis looking at viral infectivity over time, with the advantage of having one model with more power, while the ANCOVA model may give us a clearer answer if the rebound effect of viral infectivity is exponential. We will adjust for any demographic variables that are found to be significantly different between groups. We will adjust for any demographic variables that are found to be significantly different between groups.

The viral infectivity analysis will compare infectivity levels between mouth rinse types and across the time course for calculation of the reduction factor (RF calculated from PFU/mL, numerical value). The RF will be calculated as the difference in the quotient of the infection titre before (‘control titration’) and after the mouthrinse (‘remaining virus’). Therefore, the log10 titre and its (double) standard deviation (SD) were calculated as well as the variance of the RF.

Secondary Outcomes

Inflammation-associated cytokine and chemokine concentration (pg/mL) will be quantified using a Luminex bioanalyzer containing pre-validated internal standards of known concentration. Saliva and serum analyte concentrations will be compared between groups using descriptive statistics. Periodontal exam results will be reviewed to categorize patients’ periodontal status which will be reported as frequencies.

Tertiary Outcomes

The tertiary outcomes of this study are a periodontal exam and post-rinse surveys to evaluate patient perceptions of the mouthrinse, their symptoms and feedback on their willingness to use the product. Percentage of respondents will be gathered and reported for surveys. Periodontal exam data will be evaluated and the periodontal status for each participant will be assigned via the case definitions for periodontitis, gingivitis, and clinical periodontal health as described in the 2017 World Workshop

on the Classification of Periodontal and Peri-Implant Diseases and Conditions and the 2012 Centers for Disease Control and Prevention and American Academy of Periodontology case definitions.^{19, 20} Patients' final periodontal status will be the tertiary outcome of the periodontal exam and will be reported as the percentage of participants categorized into each diagnostic group.

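### Salivary cytokines are compared as changes from baseline with no stated adjustment for the pre-rinse concentration, which may cost precision that the trial could have almost for free

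*Combined protocol and SAP*

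**What the plan says.** The secondary hypothesis is that users of the sponsor's products will have lower inflammatory marker levels than controls (Sections 1.2, 10.2 Research Hypotheses and 10.5.2). Three places describe how this will be examined.

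- **Section 10.6, model.** A linear model for repeated measures "will be used to compare the changes in other continuous outcomes (such as immunological parameters) from baseline to specific time points outlined", at a two-sided 0.05 level, with Tukey adjustment across arms and a false discovery rate correction across markers. IL-6, IL-8, IL-10 and CXCL-10 are measured in samples "collected at each visit and across the salivary collection time course using multiplex analyte analysis".
- **Section 10.5.3, table of variables.** The dependent variable is "Cytokine level (continuous positive variable"). The covariates are age, gender, race and body mass index. The time factor reads "Time (in minutes, 0, 15, 30, 45 and 60 minutes, visit 1 and 2"), with no separate pre-rinse level.
- **Section 10.2 Research Hypotheses, Secondary Outcomes.** "Saliva and serum analyte concentrations will be compared between groups using descriptive statistics".

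Under Primary Outcomes in the same section, infectivity is analysed by ANCOVA at each time through "post 45 minute and post 60 minute adjusting for time Pre 0 minute". The only other adjustment rule concerns demographics: "We will adjust for any demographic variables that are found to be significantly different between groups".

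**The concern.** Pre-rinse saliva is collected from everyone (Précis; Section 3), and the analytes are measured across the saliva time course. The value needed for baseline adjustment should therefore be in hand, and the plan uses that kind of adjustment for infectivity from the same sampling scheme. For cytokines it speaks only of changes from baseline, and its covariate list has no baseline concentration.

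A raw change score subtracts the whole baseline value, whatever its correlation with the later value. Unless the correlation is very high, this adds noise that a regression on baseline would remove. The sample size of about 25 per arm was justified on infectivity alone, so nothing in the documents shows that the cytokine comparison has power to spare. At stake is the precision of a hypothesis-driven secondary comparison, and its sensitivity to a chance difference between arms at baseline.

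**Working it through.** **Inputs from the documents.** About 25 participants per arm (Sections 3 and 10.6); two-sided 0.05 with Tukey adjustment across five arms (Section 10.6). The plan states no power, SD, effect size or correlation for cytokines, so it has no figure of its own to reproduce.

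**Assumptions.** Equal variance sigma² at baseline and follow-up; correlation rho from 0.2 to 0.9; complete data; a between-arm difference of 0.7 SD. The value 0.7 is borrowed from the plan's infectivity power statement. There it is a paired, within-arm effect, so here it serves only as an illustration.

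**Variance per participant, in units of sigma².**

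- Follow-up value alone: 1.
- Raw change: 1 + 1 − 2·rho = 2(1 − rho).
- Adjusted for baseline: 1 − rho² = (1 − rho)(1 + rho).
- Ratio of adjusted to change: (1 + rho)/2.

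The change-score variance applies if the repeated measures model gives each arm its own mean at every time, including baseline.

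**Power, one rinse against water.** The noncentrality is 0.7 / √(v × 2/25), where v is the variance above. Degrees of freedom are 48 for change and 47 after baseline adjustment. At rho = 0.5:

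- Change: 0.7 / √(1.00 × 0.08) = 2.475; critical value 2.011; power 68%.
- Adjusted: 0.7 / √(0.75 × 0.08) = 2.858; critical value 2.012; power 80%.

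| rho | Change | Adjusted | Ratio | Variance lower by | Power, change | Power, adjusted |
|---|---|---|---|---|---|---|
| 0.2 | 1.60 | 0.96 | 0.60 | 40% | 48% | 70% |
| 0.3 | 1.40 | 0.91 | 0.65 | 35% | 54% | 72% |
| 0.5 | 1.00 | 0.75 | 0.75 | 25% | 68% | 80% |
| 0.7 | 0.60 | 0.51 | 0.85 | 15% | 88% | 92% |
| 0.8 | 0.40 | 0.36 | 0.90 | 10% | 97% | 98% |
| 0.9 | 0.20 | 0.19 | 0.95 | 5% | near 100% | near 100% |

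With a Tukey critical value of 2.77 (five arms, 120 df), power goes from 39% to 54% at rho 0.5, from 66% to about 75% at 0.7, and from 87% to 91% at 0.8.

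**Cost of estimating the slope.** A simulation of 20,000 trials at 25 per arm and rho 0.5 gave a variance ratio of 0.775 against the theoretical 0.75. Using 0.775, the noncentrality is 0.7 / √(0.775 × 0.08) = 2.811 and power is 79%. The gain is slightly smaller but remains.

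**Detectable difference at 80% power, rho 0.5 (normal approximation).** (1.960 + 0.842) × √(0.08) = 0.79 SD for change, and 0.79 × √0.75 = 0.69 SD after adjustment.

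**Chance imbalance.** If an arm starts D higher by chance, its expected follow-up excess is rho·D, so the change contrast is shifted by −(1 − rho)D. At 25 per arm the SD of D is √(2/25) = 0.28 SD. A one-SD imbalance at rho 0.5 therefore shifts the contrast by 0.14 SD. The shift averages to zero over randomization.

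**The case against.** **The inefficient estimator is partly inferred from silence.** Section 10.6 does not say whether baseline enters as an outcome level with free arm means, as a common mean across arms, or as a covariate, and the Section 10.5.3 table lists the level, not the change, as dependent variable. A model with a common baseline mean also yields changes from baseline and recovers about the same efficiency as adjustment. This stands: a reader might infer that the plan has chosen the raw change score, but the documents show only that baseline handling is not stated. The loss above is conditional on free arm means.

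**The inferential comparison itself is not settled.** The descriptive-statistics sentence under Secondary Outcomes conflicts with the Section 10.6 model. This also stands, and editing Section 10.6 alone would leave the conflict. It does not remove the concern, because a descriptive comparison does not adjust for baseline either.

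**The size depends on assumptions.** Most follow-up samples come within an hour of the pre-rinse sample, so a high correlation cannot be ruled out, and at 0.8 to 0.9 the gain is small. The visit 2 sample, one week later, need not share that correlation. The range must therefore be shown, and no single figure can be claimed for this trial.

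**Harm is limited.** The outcome is secondary, the plan claims no power for it, and large p-values are to be reported as inconclusive. That bears on priority; it is no reason to leave the precision unused.

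**Availability of the baseline assay.** Section 6.2.2 names only viral load and infectivity for the baseline sample. Sections 3 and 10.6 cover cytokines across the collected saliva, and a change from baseline needs that assay anyway, so this is a point to make explicit.

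**Conclusion.** The concern holds in a conditional form. Section 10.6 compares cytokines as changes from baseline, no section adjusts for the pre-rinse concentration, and the trial collects the sample that would allow it. If arm means are free at baseline, adjustment lowers the variance of the salivary contrast by 40% at rho 0.2, 25% at 0.5 (slightly less after estimating the slope), 15% at 0.7, 10% at 0.8 and 5% at 0.9. For an assumed 0.7 SD difference at 25 per arm, unadjusted power rises by about 12 points at rho 0.5, 4 at 0.7 and 1 at 0.8. Rho, the effect size and equal variances are assumptions.

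Two stronger readings are not supported. A reader might infer that the comparison is biased. It is not biased on average, because arms are assigned by block randomization; only the result given a particular chance imbalance is shifted. A reader might also take the 25% at rho 0.5 as the share of the attainable gain that is lost. It is the reduction relative to the change score. At that correlation the change score has the same variance as the follow-up value alone, so it captures none of the gain from having a baseline.

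**What to change.** Before data are analysed:

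1. In Section 10.6, state that each salivary analyte is modelled on the log scale at the post-rinse times and visit 2, with its log pre-rinse value as a covariate, plus arm, time and arm-by-time. A repeated measures model with a common baseline mean across arms is an acceptable alternative. Apply the adjustment whatever imbalance is observed.
2. Add the pre-rinse concentration to the covariate list in Section 10.5.3.
3. Define baseline as the pre-rinse sample and label it separately from time 0. Section 3 uses T_0 for the sample just after the rinse, while Section 10.4 calls 0 min baseline. Confirm in Section 6.2.2 that the pre-rinse sample is assayed for the four analytes.
4. Reconcile the descriptive-statistics sentence under Secondary Outcomes with this model.
5. Limit the adjustment to saliva. Sections 3 and 5.1 draw visit 1 blood at the end of saliva collection, after the rinse, although the table of abbreviations defines baseline blood as pre-rinse. That inconsistency also needs reconciling.

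The cost is one degree of freedom per model and a few wording edits. No added samples or participants are needed.
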